## 12.2 Analysis Conventions

For all data analyses and summary tabulations, categories for analysis and presentation are the NasoVAX and placebo groups.

Baseline is defined as the last nonmissing measurement prior to the administration of IP.

Continuous variables will be presented by geometric means and 95% CIs for the immunogenicity endpoints and by summary statistics (eg, mean, and standard deviation [SD]) for other endpoints. Categorical variables will be presented by frequency distributions (percentages and 95% CIs) for the immunogenicity endpoints and frequency counts and percentages for other endpoints.

## 12.3 Subject Disposition

The number and percentage of subjects enrolled in the study, completing the study, and discontinuing the study will be presented in a tabular format. Reasons for discontinuation will also be summarized.

Listings of randomized subjects who did not receive the IP and of subjects with other important protocol deviations (to be defined in the SAP, will be provided).

05 October 2017 Confidential Page 45 of 66

All analysis populations will be defined, and full descriptions of each population will be provided.

#### 12.4 Demographic and Bassline Characteristics

Demographic parameters and other baseline characteristics (age, gender, race, ethnicity, body mass index) will be summarized by dose group for all subjects in the Safety Population.

#### 12.5 Prior and Concomitant Medications

Prior and concomitant medications will be summarized by WHO Drug Dictionary anatomical therapeutic chemical level 3 and preferred term.

#### 12.6 Exposure

All IP doses will be summarized.

#### 12.7 Safety Analyses

The primary endpoint for evaluation of the safety profile is the number and percentage (95% CI) of subjects with solicited and unsolicited AEs recorded postvaccination. Safety analyses will be performed using the Safety Population.

### 12.7.1 Primary Endpoints

#### Reactogenicity

The number (percentage, 95% CI) of subjects with local reactions and systemic events will be summarized by dose group and overall. Reactogenicity events will also be summarized by severity.

#### **Adverse Events**

The number (percentage, 95% CI) of subjects with AEs from Day 1 to Day 29 (including MAEs, NCIs, SAEs) will be summarized for each MedDRA system organ class and preferred term and by dose group and overall. The number (percentage) of subjects with MAEs, with NCIs, and with SAEs from Day 1 to Day 181 will be summarized in a similar fashion. The number (percentage, 95% CI) of subjects with AEs by severity and by relationship to IP will also be summarized.

Listings of AEs, MAEs, NCIs, and SAEs will be provided.

## 12.7.2 Clinical Laboratory Tests and Vital Signs

Summary statistics for continuous parameters will be presented by dose group as follows: prevaccination, postvaccination, and change from prevaccination to postvaccination assessment.

The number and percentage of subjects with postvaccination clinical laboratory values or vital sign values recorded as newly abnormal (ie, an event with an increase in the toxicity grade

05 October 2017 Confidential Page 46 of 66

relative to the baseline value and with a severity grade of moderate or higher) after study vaccination will be tabulated. Shift tables which cross-tabulate the prevaccination and postvaccination clinical laboratory values of each subject by severity grade will be prepared.

### 12.7.3 Electrocardiograms

Summaries of the number and percentage of subjects with normal, abnormal not clinically significant, and abnormal clinically significant interpretations will be presented.

#### 12.7.4 Shedding of Replication-deficient Vector

Data will be summarized by count and percent positive by time point, along with median copy number.

#### 12.7.5 Laboratory-confirmed Adenovirus Infection

Viral culture results will be listed.

#### 12.8 Immunogenicity Analyses

Immunology analyses will be conducted using the ITT and PP Populations with primary conclusions drawn from the PP Population. Analyses based on the ITT Population will be undertaken and presented only if >5% of subjects in any 1 dose group were excluded from the PP Population. No imputation for missing data will be performed. Data will be transformed as appropriate prior to analysis.

Baseline is defined as the sample collected prior to IP administration on Day 1.

## 12.8.1 Secondary Endpoints (Humoral Immune Response)

The primary variable of interest for assessment of humoral immune response to the NasoVAX antigen is homologous HAI antibody titer. The following HAI immunogenicity measures and their 95% CIs will be summarized by dose group:

- GMT at baseline and postvaccination on Days 4, 8, 15, 29, 91, and 181
- GMR on Days 4, 8, 15, 29, 91, and 181 (analysis of GMR will be performed using analysis of covariance [ANCOVA] with baseline titer as a covariate)
- SPR on Days 4, 8, 15, 29, 91, and 181
- SCR on Days 4, 8, 15, 29, 91, and 181

05 October 2017 Confidential Page 47 of 66

#### 12.8.2 Exploratory Endpoints

#### **Humoral Immune Response**

Humoral immune response (antibody level measured by microneutralization in serum) will be summarized by GMT at baseline and postvaccination on Day 29 and responder rate (the proportion of subjects with 2-fold and 4-fold rise since baseline) (95% CI) on Day 29.

#### Cellular Immune Response

Cellular responses (ELISpot SFUs to influenza HA peptides) will be summarized by geometric mean at baseline and postvaccination on Day 8 and responder rate on Day 8.

#### **Mucosal Immune Response**

Mucosal responses (IgA to influenza HA peptides by ELISA) will be summarized by geometric mean at baseline and postvaccination on Day 29 and responder rate on Day 29.

#### Humoral Immune Response to Nonrepresented Influenza Strains

Humoral immune response to nonrepresented influenza strain antigens (antibody level measured by HAI and microneutralization in serum) against each strain tested will be summarized by GMT at baseline and postvaccination on Day 29; GMR postvaccination on Day 29; and responder rate (the proportion of subjects with 2-fold and 4-fold rise since baseline) on Day 29.

#### Effect of Predose Adenovirus Serotype 5 Serum Antibody Levels on Immunogenicity

For the effect of predose Ad5 serum antibody levels on immunogenicity of NasoVAX on Day 29, analysis will be performed using ANCOVA, with baseline Ad5 titer as a covariate.

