#### **Immunogenicity**

Immunology analyses will be conducted using the Intent-to-treat (ITT) and Per-protocol (PP) Populations with primary conclusions drawn from the PP Population. Analyses based on the ITT Population will be undertaken and presented only if >5% of subjects in any 1 dose group were excluded from the PP Population. No imputation for missing data will be performed. Data will be transformed as appropriate prior to analysis.

Baseline is defined as the sample collected prior to IP administration on Day 1.

The primary variable of interest for assessment of humoral immune response to the NasoVAX antigen is homologous HAI antibody titer. The following HAI immunogenicity measures and their 95% CIs will be summarized by dose group:

- GMT at baseline and postvaccination on Days 4, 8, 15, 29, 91, and 181
- GMR on Days 4, 8, 15, 29, 91, and 181 (analysis of GMR will be performed using analysis of covariance [ANCOVA] with baseline titer as a covariate)
- SPR on Days 4, 8, 15, 29, 91, and 181
- SCR on Days 4, 8, 15, 29, 91, and 181

Humoral immune response as measured by microneutralization in serum will be summarized by GMT at baseline and postvaccination on Day 29 and responder rate (the proportion of subjects with 2-fold and 4-fold rise since baseline) (95% CI) on Day 29.

Cellular responses (ELISpot SFUs to influenza HA peptides) will be summarized by geometric mean at baseline and postvaccination on Day 8 and responder rate on Day 8.

Humoral immune response to nonrepresented influenza strain antigens (antibody level measured by HAI and microneutralization in serum) against each strain tested will be summarized by GMT at baseline and postvaccination on Day 29; GMR postvaccination on Day 29; and responder rate (the proportion of subjects with 2-fold and 4-fold rise since baseline) on Day 29.

For the effect of predose Ad5 serum antibody levels on immunogenicity of NasoVAX on Day 29, analysis will be performed using ANCOVA, with baseline Ad5 titer as a covariate.

Immunogenicity results from samples collected in this study will be compared to those from banked samples from a previous study of licensed seasonal vaccine in a similar subject population using a 2-sample comparison of means or nonparametric tests as indicated.

05 October 2017 Confidential Page 13 of 66

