#### 2.3 NasoVAX

Adenovirus is a naturally occurring respiratory virus that has been used frequently as a vector to introduce genetic material into cells. By incorporating the influenza HA gene into replication-deficient (RD) adenovirus (Ad-HA) and applying the Ad-HA into the nose, the adenoviral vector can transduce the HA gene into cells of the nasal mucosa, leading to transient expression of the encoded HA protein. An immune response to the expressed HA antigen can thus be induced. Thus, RD Ad-HA constructs hold potential as a novel type of influenza virus vaccine that does not require administration by needle injection.

NasoVAX is based on Altimmune's RespirVec platform, an RD-Ad5 vector that expresses the protein of interest within respiratory epithelial cells. In the case of NasoVAX, the vector contains a genetic insert encoding the HA surface protein antigen from influenza type A or B. The

05 October 2017 Confidential Page 16 of 66

RespirVec platform has the potential to provide a more rapid production system than egg-based vaccines. In previous nonclinical and clinical studies, NasoVAX does not appear impeded by prior existing adenoviral immunity and generates strong antibody and cellular immune responses. In an animal challenge model, NasoVAX protected against highly divergent influenza strains and was protective within days of administration.

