#### 2.6 Clinical Trials of NasoVAX

The immunogenicity and safety of Ad-5 vectored influenza vaccines has been evaluated in 2 Phase 1 studies in healthy volunteers. These studies involved doses similar to the lowest dose being delivered in the this study or lower. The vaccines were well tolerated. Immune responses were weak but measurable despite the relatively low doses tested. The trials are summarized below, and additional details are provided in the current Investigator Brochure.

In a 2002 study of an Ad5-vectored vaccine encoding the HA surface protein antigen from the A/Puerto Rico/8/34(H1N1) strain of influenza of 24 male health volunteers aged 20 to 31 years, 6 subjects received 2 intranasal doses of  $5 \times 10^8$  vp 28 days apart [Van Kampen 2005]. In addition to the intranasal vaccine recipients, 18 other subjects received 2 topical doses of either  $4.8 \times 10^9$ ,  $4.8 \times 10^{10}$ , or  $4.8 \times 10^{11}$  vp. No SAEs or severe AEs were observed. For both administration sites, most (85%) of the side effects were mild in severity, 15% were moderate, and no serious reactions to the vaccine were observed either systemically or at the site of inoculation. The local

05 October 2017 Confidential Page 18 of 66

AEs reported in the intranasal group were discoloration (1 subject), burning (2 subjects), and bitter taste (1 subject). Systemic events of soreness, headache, nausea/vomiting, and muscle pain were reported for 1 subject each in the intranasal group. Four of the 6 subjects who received the intranasal vaccine had increased HAI antibody titers after the primary dose, and this number increased to 5 after the booster dose. No correlation was observed between prevaccination Ad5 antibody titers and HAI titer fold changes for intranasal administration.

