# **3 STUDY OBJECTIVES AND ENDPOINTS**

OBJECTIVES	ENDPOINTS			
Primary Objective				
• To describe the safety profile of NasoVAX in healthy adults when administered by intranasal spray at a single dose of 1×10  , 1×10  , or 1×10  vp	
 
Reactogenicity: counts and percentages of subject with local events (nasal irritation, sneezing, nasal congestion, cough, sore throat, change in smell, change in taste, change in vision, eye pain) and systemic events (headache, fatigue, muscle ache, nausea, vomiting, diarrhea, chills, fever) for 14 days after vaccination
 
AEs: counts and percentages of subjects with AE from Day 1 to Day 29; MAEs, SAEs, NCIs from Day 1 to Day 181
 
			
Secondary Objective				
• To evaluate the humoral immune response to NasoVAX when administered by intranasal spray at a single dose of 1×10  , 1×10  , or 1×10  vp	
 
Antibody level measured by HAI in serum:         
 
GMT: the antilog of the mean of the log-transformed titers
 
GMR: the ratio of postvaccination and prevaccination GMTs within the same dose group
 
SPR: the percentage of subjects with a HAI titer ≥ 1:40
 
SCR: the percentage of subjects with either a baseline HAI titer < 1:10 and a postvaccination titer ≥ 1:40 (which is 4 times the assay lower limit of quantitation), or a baseline HAI titer ≥ 1:10 and a 4-fold increase in postvaccination HAI titer relative to baseline
 
 
 
Antibody level measured by microneutralization in serum:         
 
GMT
 
Responder rate: the proportion of subjects with 2-fold and 4-fold rise since baseline
 
 
 
			

OBJECTIVES	ENDPOINTS			
Exploratory Objectives				
• To evaluate the cellular immune response to NasoVAX when administered by intranasal spray at a single dose of 1×10  , 1×10  , or 1×10  vp	
 
SFUs to HA peptides measured by enzyme-linke ELISpot in PBMCs:
 
Geometric mean SFUs
 
Responder rate
 
			
• To evaluate the mucosal immune response NasoVAX when administered by intranasal spray at a single dose of 1×10  , 1×10  , or 1×10  vp	
 
IgA antibody level measured by ELISA:
 
GMT
 
GMR
 
			

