To evaluate the humoral immune response against nonrepresented influenza strains after NasoVAX administration	
 
Antibody level measured by HAI and microneutralization in serum against each strain tested:         
 
GMT
 
GMR
 
Responder rate: the number and percentage of subjects with 2-fold and 4-fold rise since baseline
 
 
 
			
To evaluate the effect of predose Ad5 serum antibody levels on the immunogenicity of NasoVAX	
 
Predose Ad5 antibody GMT measured by microneutralization in serum
 
Day 29 GMR and responder rate from antibody level measured by HAI in serum
 
			
To compare immunogenicity results to those obtained from banked samples from a previous study of licensed seasonal vaccine in a similar subject population	
 
Antibody level measured by HAI in serum:         
 
GMT
 
GMR
 
SPR
 
SCR
 
 
 
Antibody level measured by microneutralization in serum:         
 
GMT
 
Responder rate
 
 
 
SFUs to hemagglutinin peptides measured by ELISpot in PBMCs:         
 
Geometric mean SFUs
 
Responder rate
 
 
 
			
	
 
IgA antibody level measured by ELISA:
 
GMT
 
GMR
 
			

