- 18. Immunocompromised individuals, including those who have used corticosteroids (including intranasal steroids), alkylating drugs, antimetabolites, radiation, immune-modulating biologics, or other immunomodulating therapies within 90 days before Day 1 or those who plan use during the study period
- 19. Use of statin medication within 30 days before Day 1 (see list in Section 6.8.1)
- 20. Receipt of intranasal medications (including over-the-counter medications) within 30 days before Day 1
- 21. Receipt of any IP within 30 days before Day 1
- 22. Receipt of any vaccine within 30 days before Day 1
- 23. Receipt of intranasal vaccine within 90 days before Day 1
- 24. Receipt of any influenza vaccine within 6 months before Day 1
- 25. Any change in medication for a chronic medical condition within 30 days before Day 1
- 26. Past regular use or current use of intranasal illicit drugs
- 27. Smokers, including smoking of any type (eg, cigarettes, electronic cigarettes, marijuana). Prior smokers must have quit smoking at least 30 days before Day 1.
- 28. Any medical, psychiatric, or social condition or occupational or other responsibility that in the judgment of the Investigator would interfere with or serve as a contraindication to protocol adherence, assessment of safety (including reactogenicity), or a subject's ability to give informed consent

05 October 2017 Confidential Page 27 of 66

[figure not shown]

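### The exploratory Ad5 analysis names baseline Ad5 titer but not baseline HAI titer, and no model is named for the binary HAI responder rate

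*Protocol*

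**What the plan says.** Section 12.8.2 gives one sentence on the effect of predose Ad5 antibody: "analysis will be performed using ANCOVA, with baseline Ad5 titer as a covariate". The synopsis (Section 1.1) repeats it: "For the effect of predose Ad5 serum antibody levels on immunogenicity of NasoVAX on Day 29, analysis will be performed using ANCOVA". Neither place names a second covariate, a dose term or a second method.

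Section 3 lists two Day 29 outcomes under this objective: "Day 29 GMR and responder rate from antibody level measured by HAI in serum". The GMR is continuous on the log scale. Responder status is yes or no for each subject.

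Section 12.8.1 treats the HAI GMR, Day 29 included, as follows: "analysis of GMR will be performed using analysis of covariance [ANCOVA] with baseline titer as a covariate". Because this stands in the list of HAI measures, the baseline titer meant there is the HAI titer.

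Baseline HAI titer can be expected to vary. Eligibility sets no titer limit. The influenza-specific vaccine exclusion is "Receipt of any influenza vaccine within 6 months before Day 1", and the seroconversion definition provides for subjects with "a baseline HAI titer ≥ 1:10 and a 4-fold increase in postvaccination HAI titer relative to baseline".

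**The concern.** GMR is a ratio of postvaccination to prevaccination titers, so baseline HAI titer is part of the outcome. A rise that depends on baseline puts that dependence into the residual when baseline is left out. If Ad5 and HAI baselines also correlate, it goes into the Ad5 slope.

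The question matters to the programme. Section 2.3 says that "NasoVAX does not appear impeded by prior existing adenoviral immunity". Section 2.6 supports this with two null results. In the first study, with 6 intranasal recipients, "No correlation was observed between prevaccination Ad5 antibody titers and HAI titer fold changes for intranasal administration". The second, with 36 active recipients (48 randomized less 12 on placebo), also reports no association. This trial looks again in 45 recipients. A noisy slope could be read as further reassurance, and a confounded one could point either way.

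For responder status, ANCOVA is the only method named under the objective, and it is not a natural model for a yes/no outcome.

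**Working it through.** **The plan's own figure.** There is none for this analysis. Section 12.9 says that the sample size was not chosen for power. Everything below is conditional on assumed inputs.

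**Inputs.**
- From the protocol: 45 NasoVAX recipients, 15 per dose.
- Assumed, log2 scale: Ad5 SD 1, baseline HAI SD 1.5, residual SD 1.2; the rise changes by b = -0.5 or -0.3 per log2 of baseline HAI; dose is a 3-level factor in both models; r is the correlation of the two baseline titers. The outcome is the log2 fold rise.

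**Precision at r = 0.** Without baseline HAI the residual variance is 1.2² + b² × 1.5².
- b = -0.5: 1.44 + 0.5625 = 2.0025; ratio 2.0025/1.44 = 1.391.
- b = -0.3: 1.44 + 0.2025 = 1.6425; ratio 1.6425/1.44 = 1.141.

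Adjusting costs one degree of freedom, a factor of 39/40. The slope variance ratios become 1.356 and 1.112. Simulation (20,000 trials per setting) gave 1.34 and 1.11. For a true slope of -0.5 log2 per Ad5 SD, simulated power is 60% or 68% without baseline HAI and 72-73% with it.

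**Bias when the titers correlate.** Bias of the Ad5-only slope = b × r × 1.5 (Ad5 SD is 1).
- r = 0.3, b = -0.5: -0.5 × 0.3 × 1.5 = -0.225.
- r = 0.3, b = -0.3: -0.3 × 0.3 × 1.5 = -0.135.

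| Setting | Ad5-only model | With baseline HAI |
|---|---|---|
| r = 0.3, true slope 0: false positives | about 18% (b = -0.5), 10% (b = -0.3) | 5% |
| r = -0.3, true slope -0.5: mean slope | -0.27, -0.37 | unbiased |
| r = -0.3, true slope -0.5: power | 24%, 44% | 69% |

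The precision argument weakens as r grows, because the adjusted slope pays a factor 1/(1 - r²). At r = 0.3 the variance ratio is [1.44 + b² × 2.25 × 0.91]/1.44 × 39/40 × 0.91. That is 1.20 for b = -0.5 and 1.00 for b = -0.3. There the problem is bias.

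**A case that favours the Ad5-only model.** Suppose the apparent dependence on baseline is only assay error (reliability 0.85, r = 0.3, true slope 0). The adjusted slope is then off by about +0.07, with 5.9% false positives, and the Ad5-only slope on the fold rise is unbiased.

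**Responder status.** Take the same responder probability p in each dose group. The chance that at least one of three groups of 15 has no responder is 1 - (1 - (1 - p)^15)^3.
- p = 1/12 (8.3%): 0.917^15 = 0.271, giving 0.61.
- p = 0.20: 0.8^15 = 0.035, giving 0.10.
- p = 1/3: 0.667^15 = 0.0023, giving 0.007.

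The 8.3% is the seroconversion rate in the highest dose group of the 2007 study in Section 2.6. The 33% is the share of that group with any rise in HAI titer. At the low end, ordinary logistic regression with a dose factor would often fail to give finite estimates.

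**The case against.** The case against is substantial, and most of it stands.

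- **Deferral.** Section 12 calls itself brief and leaves detail to an SAP, which could settle this. That limits the severity. But here the protocol does state a method and a covariate, in two places, so the sentence can be judged as written.
- **No exclusion.** A reader might infer that the protocol rules out baseline HAI adjustment and so contradicts Section 12.8.1. It does not. The text speaks of a covariate, not the only one, and adding Ad5 titer to the Section 12.8.1 model is a natural reading. Neither section names a dose term either, and the working above supplies one.
- **Responder rate.** A reader might infer that ANCOVA will be run on a 0/1 variable. Section 12.8.2 never says so, and Section 12.2 presents categorical immunogenicity variables as percentages with 95% CIs. The supportable statement is that no model linking Ad5 titer to responder status is named.
- **Size.** No titer SD, slope or correlation is in the protocol, and other assumptions give other figures. With SDs of 2 for both titers and residual SD 1, false positives at r = 0.4 are 26-46%. The earlier responder rates come from an H5N1 construct at 3.3×10^9 vp, and this trial goes up to 1×10^11 vp.
- **Adjustment is not always better.** The assay-error case shows this, so the second slope should be kept.

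**Conclusion.** The concern holds as a minor gap in specification. The one sentence given for the Ad5 objective does not carry over the baseline HAI adjustment that the protocol applies to the same outcome, and it leaves the binary outcome without a suitable model. Taken literally, and under the stated assumptions, it costs about 4 to 13 points of power at zero correlation. At a correlation of 0.3 in either direction it can create or mask an Ad5 association. If the baselines are uncorrelated, only precision is lost.

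Nothing here shows that the earlier null findings on Ad5 immunity are wrong, or that this trial's result would be. The analysis is exploratory. The primary safety objective, the sample size and dose escalation do not depend on it.

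**What to change.** Replace the sentence in Section 12.8.2 and the synopsis with wording to this effect:

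*In NasoVAX recipients, log Day 29 HAI titer will be modelled on log baseline Ad5 titer, log baseline HAI titer and dose group. The Ad5 slope will be reported with its 95% CI. The slope from the model for log fold rise without baseline HAI titer will be shown beside it as a sensitivity analysis. HAI responder status will be related to baseline Ad5 titer by exact or penalised logistic regression.*

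With baseline HAI in the model, the Ad5 slope is the same for log Day 29 titer and log fold rise. Without it the two differ, so the sensitivity model should name the fold rise, which matches the GMR endpoint. The responder threshold can be named in the same place, since this objective's entry gives none.

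The cost is wording only. Day 1 HAI and Ad5 titers and dose group are already collected, and the change can be made before the interim database snapshot.
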